1 STUDY SYNOPSIS

Provide brief information

Title:	Investigation and Comparison of the Antibody Response initiated by Recombinant, Cell-Based and Egg-Based Influenza Vaccines
Short Title:	Immunogenicity trial of 3 influenza vaccines
Design:	Randomized controlled trial
Study Centre:	National Centre for Infectious Diseases (NCID), Singapore; WHO Collaborating Centre for Reference and Research on Influenza
Hospital:	National Centre for Infectious Diseases Research Clinic
Study Question:	Does recombinant vaccine result in a better antibody response than either standard egg-grown vaccine or cell-grown vaccine?
Primary objective:	To assess whether vaccination with recombinant quadrivalent influenza vaccine (QIV-R) results in a better antibody response against A(H3N2) viruses than either standard egg-grown vaccine (QIV-E) or cell-based vaccine (QIV-C) as measured by post-vaccination geometric mean titre from the haemagglutination inhibition assay
Secondary objectives	
1. To estimate whether antibody responses to all 4 vaccine antigens are greatest in participants who received QIV-R and least in participants who received QIV-E, and if this reflects greater cell- to egg-grown antibody titre ratios.2. To estimate whether QIV-R induces antibodies against a greater genetic and antigenic range of A(H3N2) viruses than QIV-C and QIV-E.3. To estimate whether prior vaccination history has less effect on antibody responses induced against all 4 vaccine antigens by QIV-R compared with QIV-C and QIV-E.4. To estimate whether antibody titres against all 4 vaccine antigens are better maintained up to 12 months after vaccination with QIV-R compared with QIV-C and QIV-E.5. To estimate whether QIV-R induces higher frequencies of HA reactive B cells and/or B cells with different HA cross-reactivity profiles and phenotypes compared with QIV-C and QIV-E.6. To assess whether QIV-R offers better protection against infection compared with QIV-C or QIV-E.
Inclusion Criteria:	
1. Aged ≥ 21 years and < 50 years.2. Able to provide informed consent

Study Name: Immunogenicity trial of 3 influenza vaccine [VAP3]

Protocol Number: 2021.247

DSRB Ref Number: 2022/00275

Version & date: version 2.0, dated 27 Oct 2022

Page 6 of 38

	
 3. Willing and able to provide 4 blood samples: 
 3.1. just prior to vaccination (V1), 3.2. 14–21 days post vaccination (V2) 3.3. 4–6 months post-vaccination (V3) 3.4. 10-12 months post-vaccination (V4) 4. Has not received influenza vaccine for at least 6 months before enrolment 5. Willing to provide current mobile phone number for SMS reminders
Exclusion Criteria:	
 1. Known contraindication(s) for QIV (e.g. hypersensitivity to vaccine component (including eggs)). 2. Recently (last 7 days) or currently ill or has a fever above 38°C. 3. Cannot recall if they were vaccinated against influenza during more or less than two of the preceding five years. 4. Hypogammaglobulinaemia or immunoglobulin replacement 5. Undergoing immuno-suppressive therapies
Number of Planned Subjects:	360
Investigational products:	FluBlok® FlucelVax® Quad Fluarix® (or equivalent egg-grown QIV)
Safety considerations:	The risk of an adverse event associated with, influenza vaccination, blood collection and collection of nasal swab(s) is low. Any adverse event will be recorded and followed up by the project manager or principal investigator.
Statistical Methods:	
Baseline comparisons: Baseline data will be summarised by vaccination group, with each arm.
 
Analysis of the primary objective: The post-vaccination geometric mean titres (GMT) by vaccination regimen will be compared by using mixed-effects linear regression.

Subgroups:	
 A. Frequently vaccinated (vaccinated during 3-5 of the preceding five years) B. Infrequently vaccinated (vaccinated during 0 or 1 of the preceding five years)

2 GLOSSARY OF ABBREVIATIONS & TERMS

Abbreviation	Description (using lay language)
AE	Adverse event
AR	Attack rate
ARI	Acute respiratory infection At least one respiratory symptom (cough, sore throat) and one systemic symptom (fever, malaise, fatigue, myalgia)
AESI	Adverse event of special interest
GCP	Good clinical practice
GMT	Geometric mean titre Arithmetic mean of the logarithms (base 2) of the last positive dilution of each serum
GMR	GMTR geometric mean titre ratio Arithmetic mean of the logarithms (base 2) of the last positive dilution of each serum
HA	Haemagglutinin The surface protein of the influenza virus that is targeted by vaccines.
HAI	Haemagglutination inhibition assay Laboratory test, which measures anti-haemagglutinin antibodies. These antibodies inhibit attachment of the influenza virus to target cell membrane receptors on red blood cells.
Frequently vaccinated	3 or more prior influenza vaccinations during the past 5 years
IDRL	Infectious Diseases Research Laboratory, National Centre for Infectious Diseases, Singapore
IM	Intramuscular
Infrequently vaccinated	One or no prior influenza vaccinations during the past 5 years
ITT	Intention to treat
NCID	National Centre for Infectious Diseases, Singapore
NPHL	National Public Health Laboratory, National Centre for Infectious Diseases, Singapore

Study Name: Immunogenicity trial of 3 influenza vaccine [VAP3]

Protocol Number: 2021.247

DSRB Ref Number: 2022/00275

Version & date: version 2.0, dated 27 Oct 2022

Page 8 of 38

PI	Principal investigator
PICF	Participant informed consent form
PP	Per protocol
QIV	Quadrivalent influenza vaccine
QIV-C	Cell-based quadrivalent influenza vaccine
QIV-E	Egg-based quadrivalent influenza vaccine
QIV-R	Recombinant quadrivalent influenza vaccine
SAE	Serious adverse event
SAP	Statistical analysis plan
Seroconversion	Evidence of a 4-fold increase in antibody titre post-vaccination, as measured using a haemagglutination inhibition or microneutralisation assay
Seropositive	Antibody titre of ≥ 40 , as measured using a haemagglutination inhibition assay
TTSH	Tan Tock Seng Hospital, Singapore
WHO	World Health Organization
WHOCCRRI	World Health Organization Collaborating Centre for Reference and Research on Influenza

4 INTRODUCTION/BACKGROUND INFORMATION

4.1 LAY SUMMARY

The proposed study is a prospective randomised trial of 3 influenza vaccine formulations with different manufacturing processes: 1) egg-grown; 2) cell-grown; and 3) recombinant protein. The main objective is to compare the antibody responses following influenza vaccination among these 3 vaccines to determine whether recombinant vaccines offer superior protection over standard egg or cell-based formulations. Because antibody responses to influenza vaccines can differ depending on how many times you have been vaccinated before, we will test these 3 vaccines in 2 groups: A) frequently vaccinated (3 or more vaccinations) and B) infrequently vaccinated (0 or 1 prior vaccinations) participants. Participants will be stratified by their prior vaccination history (frequent or infrequent) and randomised to 3 trial arms receiving one dose of one of the vaccines (egg-grown, cell-grown or recombinant influenza vaccines); i.e. 2 groups \times 3 vaccines. Pre- and post-vaccination blood samples will be collected to assess antibody responses to vaccination and to assess changes to the cells that make antibodies. Responses to the 3 vaccines will be compared to assess which vaccine elicits the best antibody response in both infrequently and frequently vaccinated participants.

4.2 INTRODUCTION

Influenza vaccine effectiveness varies from year to year and is generally poorest against A(H3N2), the virus subtype for which genetic and antigenic evolution among circulating strains has been greatest. While vaccination may stimulate robust antibody responses to vaccine antigen, the breadth of antibodies generated may be insufficient to protect vaccinees from infection by all circulating viruses. Furthermore, in persons repeatedly vaccinated vaccine-induced antibody responses may become blunted over time.

In recent years, problems associated with egg-based production of vaccine strains have exacerbated these problems. Influenza viruses generally acquire substitutions within the hemagglutinin (HA) protein to adapt to growth in eggs. In the case of A(H3N2) viruses these adaptations often render them antigenically distinct from the wild-type virus. Subsequently, antibodies induced against egg-adapted epitopes in the vaccine will provide limited protection against infection by circulating viruses, and vaccine effectiveness has been very low. The use of vaccine manufacturing processes that avoid growth in eggs can potentially overcome egg-focusing but may not illicit a broader antibody response.

Cell-based vaccines have been developed which can overcome some of the problems associated with egg manufacturing. One cell-based vaccine product currently licensed in Australia is Seqirus' Flucelvax Quad. As with standard dose egg-based vaccines, this product contains 15 μ g of each of the 4 recommended influenza virus antigens. Early studies suggest that cell-based vaccine may perform better against standard-dose egg-based vaccines (1-4).

Both egg and cell-based vaccines rely on the same production method for >70 years, which depends upon the growth and purification of live viruses that must be inactivated and split before being formulated into vaccines (5-7). The chemical inactivation process requires substances that cause significant disruption to key vaccine proteins (including HA) and have been found to alter the vaccines' antigenicity via crosslinking antigens and disrupting native epitopes (5, 8-12). Disruption of key antigenic structure is likely to impact vaccine efficacy (9). Recombinant vaccines offer an alternative manufacturing pathway. The Sanofi recombinant vaccine Flublok® uses a recombinant technology to produce purified HA from a baculovirus overexpression system. The HA molecule produced in an insect cell line is in an un-cleaved form, known as HA0, i.e. a form that is unable to mediate endosomal and viral membrane fusion. Importantly the manufacturing process does not require any chemical inactivation, meaning that the HA proteins are not exposed to any potential cross-linking agents that may alter antigenicity of the vaccine (6). In addition, Flublok® contains a higher concentration of antigen than standard-dose vaccines with 45 µg of each antigen included.

Recent clinical evidence has shown Flublok® to have superior efficacy over traditional cell-based influenza vaccine (13), an immunogenicity profile comparable to Fluzone® high dose in older adults (14) and superior antibody driven viral neutralisation compared to other cell-based vaccines (1, 3, 4). Another recent comparative analysis of antibody response from healthy adults (18-49 years old), comparing egg-based, cell-based and recombinant (Flublok®) vaccines found that Flublok® resulted in significantly higher titres of neutralizing antibody (1). This study used *in vitro* neutralisation assays to evaluate the antibody function and again indicates that the recombinant vaccine may have properties that allow for better viral neutralisation compared to traditional cell-based vaccines. As such clinical efficacy gains could be associated with differences between the HA in the different vaccines.

4.2.1 STUDY OVERVIEW

This study will be conducted in 360 adults, aged 21-49 years in Singapore to generate immunogenicity data. It will be a randomized, modified double-blind study comparing the immunogenicity of recombinant quadrivalent influenza vaccines (QIV-R) against egg-based (QIV-E), and cell-based (QIV-C) vaccines. This study is powered to primarily assess the immunogenicity (as assessed by hemagglutination inhibition (HAI) geometric mean titres (GMTs) at 14-21 days post-vaccination) of QIV-R compared with QIV-E, and will also assess QIV-R compared with QIV-C.

Given the acceptable safety data generated from the millions of doses of licensed QIV-R administered in the US and elsewhere and the fact that we will source this product from the US, it is considered that the risk/benefit ratio is appropriate for the conduct of a clinical study with QIV-R.

5 AIMS AND HYPOTHESES

5.1 STUDY AIM

The broad aim of the proposed study is to estimate whether vaccination with recombinant quadrivalent influenza vaccine (QIV-R) results in a better antibody response against A(H3N2) viruses than either standard egg-grown vaccine (QIV-E) or cell-based vaccine (QIV-C).

5.2 HYPOTHESES

1. As recombinant vaccine includes a higher dose of antigen and does not use egg-based manufacturing, vaccination with recombinant vaccine results in better antibody responses, particularly against A(H3N2) viruses, than either standard egg-grown vaccines or cell-grown vaccines.
2. Vaccine induced titres against influenza A(H3N2) viruses (~ wild-type), will be highest amongst recipients of recombinant vaccine, and lowest amongst recipients of standard egg-based vaccine because antibody responses are miss-directed towards egg-adapted epitopes in the latter.
3. The dose and form of recombinant vaccine means that it induces antibodies against a broader range of epitopes than the egg- and cell-grown vaccine. In turn, this will increase the range of strains against which vaccine-induced antibodies cross-react because some of these epitopes are conserved.
4. The attenuating effects of prior vaccination (~pre-existing immunity) on vaccine immunogenicity are alleviated using recombinant vaccine because higher doses of antigen allow new B cell responses to be induced in addition to recalling memory responses.

6 OBJECTIVES AND OUTCOMES

6.1 PRIMARY OBJECTIVE

To assess whether vaccination with recombinant quadrivalent influenza vaccine (QIV-R) results in a better antibody response against A(H3N2) viruses than either standard egg-grown vaccine (QIV-E) or cell-based vaccines (QIV-C) as measured by post-vaccination geometric mean titre from the haemagglutination inhibition assay.

Corresponding outcome measures:

1. Post vaccination GMT in each vaccination group, adjusted for vaccination history and baseline titre.
2. Difference in log-titres between the QIV-R and QIV-E, adjusted for vaccination history and baseline titre.
3. Difference in log-titres between the QIV-R and QIV-C, adjusted for vaccination history and baseline titre.

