13.2 SAMPLE SIZE ESTIMATION & JUSTIFICATION

The sample size is calculated considering the primary objective to test whether QIV-R offers superior immunogenicity independent of vaccination history. Our estimates for post-vaccination HI titres are based on a study among elderly adults in Hong Kong, comparing QIV-R and QIV-E (20) and is similar to the estimated sample size based on similar HI titres in a study of 18-49 year olds (21).

A sample was simulated under the following model, informed by the published estimates:

$$titre_{t=2} = titre_{t=1} + vax_R + vax_C + priorvax + vax_R \times priorvax + vax_C \times priorvax$$

(titre_{t=2} = post vaccination log titre; titre_{t=1} = post-vaccination log titre for QIV-E infrequent vaccination; vax_R = QIV-R vaccinated; vax_C = QIV-C vaccinated)

For the test of a superior A(H3N2) response among vaccinees receiving QIV-R versus QIV-E or QIV-C (one-sided test for the parameter vax_{recomb}) and assuming $\alpha=0.05$, $\beta=0.2$, the sample needed to test these effects is around 55 per arm per vaccination history. Accounting for 10% attrition, the target sample for recruitment will be 60 per arm per vaccination history.

	Infrequently vaccinated	Frequently vaccinated	Total
QIV-R	60	60	120
QIV-E	60	60	120
QIV-C	60	60	120
Total	180	180	360

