13.3 POWER CALCULATIONS

Power calculations were simulation-based. The following model was used for the simulations:

$$\logtitre_{t=2} = b_0 + b_{baseline} \logtitre_{t=1} + b_{priorvax} priorvax + b_C vax_C + b_R vax_R + b_{C-add} vax_C priorvax + b_{R-add} vax_R priorvax + e$$

The following table contains the interpretation of all model terms.

Term	Interpretation
logtitre _{t=2}	Post-vaccination log-titre.
b ₀	Expected post-vaccination log-titre for baseline log-titre 0, infrequent prior vaccination, vaccinated with QIV-E.

b_{baseline}	Expected increase in the post-vaccination log-titre for a 1-unit increase in the pre-vaccination log-titre. Adjusted for prior vaccination frequency and vaccine received.
$\log\text{titre}_{t=1}$	Pre-vaccination log-titre.
b_{priorvax}	Expected difference in the post-vaccination log-titre between the frequently and infrequently vaccinated. Adjusted for baseline titre.
priorvax	0=Infrequent prior vaccinations. 1=Frequent prior vaccinations and vaccine received.
b_C	Expected difference in post-vaccination log-titre between QIV-E and QIV-C. Adjusted for baseline titre and prior vaccination frequency.
vax_C	0=Not vaccinated with QIV-C. 1=Vaccinated with QIV-C.
b_R	Expected difference in post-vaccination log-titre between QIV-E and QIV-R vaccine. Adjusted for baseline titre and prior vaccination frequency.
vax_R	0=Not vaccinated with QIV-R. 1=Vaccinated with QIV-R.
$b_{C\text{-add}}$	Expected additional effect of QIV-C in the frequently vaccinated.
$b_{R\text{-add}}$	Expected additional effect of QIV-R in the frequently vaccinated.
e	Random error

The following table contains the values used for the parameters in the model (subsequent tables will show deviations if there are any).

Term	Value
b_0	1.1
b_{baseline}	0.8
b_{priorvax}	-0.2
b_C	0.25
b_R	0.5
$b_{C\text{-add}}$	0
$b_{R\text{-add}}$	0.2

In each simulation there was an equal number of subjects in each arm and vaccination history group. Baseline log-titres were simulated from $N(3.7, 1)$ which produced a distribution representative of the baseline titre data of published studies. The error term was sampled from $N(0, 1)$ which produces post-vaccination titre distribution representative of published studies.

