The model simulates a subject's post-vaccination titre given their pre-vaccination titre, prior vaccination status (frequent or infrequent) and the vaccine they were given (QIV-R, QIV-C, QIV-E). The effect of the vaccines was allowed to vary between frequently and infrequently vaccinated.

Simulations were performed with different per-group sample sizes and different effects of QIV-R (b_R). For the purposes of fitting the model to the simulated data, all titres were censored to the appropriate interval (<10, 10-20, 20-40 up to 5260-10240 on the original titre scale) to simulate real measurements. The model was then fit using the midpoints of the intervals except <10 which was censored to 5 (as it would be for real data).

There were 5000 simulations for each sample size and value of b_R . Each simulated dataset was used to fit a model (the same one that was used to simulate it). The primary outcome measure was taken to be the effect of the QIV-R as compared to the QIV-E (i.e., the expected difference in post-vaccination log-titres between the QIV-R and QIV-E,) which corresponds to the b_R parameter in the model. A one-sided and a two-sided test was performed on the b_R estimate for each simulation. The "power" is the proportion of simulated studies that showed that b_R is significantly greater than 0. The results are in the table below.

Per-arm per-vaccine history sample size	True b_R (expected ratio between QIV-R and QIV-E)	Proportion with significant (one-sided) positive b_R	Proportion with significant (two-sided) positive b_R
50	0.5 (1.65)	0.772	0.665
55	0.5 (1.65)	0.810	0.712
60	0.5 (1.65)	0.832	0.741
70	0.5 (1.65)	0.889	0.807
80	0.5 (1.65)	0.920	0.858
200	0.25 (1.28)	0.775	0.676
220	0.25 (1.28)	0.810	0.717
240	0.25 (1.28)	0.834	0.742

Power of 80% can be achieved (for a one-sided test) with approximately 55 subjects per arm/per vaccine history given the true effect of 0.5 (true expected ratio 1.65). The total sample required would be approximately 330 subjects. This equates to 74% power for a two-sided test.

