13.4.1 PRIMARY OBJECTIVE

To assess whether vaccination with recombinant quadrivalent influenza vaccine (QIV-R) results in a better antibody response against A(H3N2) viruses than either standard egg-grown vaccine (QIV-E) or cell-based vaccine (QIV-C) as measured by post-vaccination geometric mean titre from the haemagglutination inhibition assay

Post-vaccination GMTs will be calculated for each group using the model described in 13.3, in which the outcome is an individual's post-vaccination titre, estimated given their pre-vaccination titre, prior vaccination status (frequent or infrequent) and the vaccine they were given (QIV-R, QIV-C, QIV-E). A t-test (on a model parameter) will be used to assess statistical significance of the effects of QIV-R versus QIV-E and QIV-C.

13.4.2 SECONDARY OBJECTIVE 1

To estimate whether antibody responses to all 4 vaccine antigens are greatest in participants who received QIV-R and least in participants who received QIV-E, and if this reflects greater cell- to egg-grown antibody titre ratios.

The post-vaccination vs pre-vaccination **log-titre difference** (geometric mean ratio) will be compared using linear regression with the explanatory variable being the type of vaccine (reference QIV-E, separate parameter for QIV-R and QIC-C). A t-test will be used to assess statistical significance of the effects of QIV-R and QIC-C (as compared to reference) as well as the difference in those effects.

The post-vaccination **seropositivity** (coded as 1 if the post-vaccination titre is at least 40, 0 otherwise) will be compared using logistic regression with the explanatory variable being the type of vaccine (reference QIV-E, separate parameter for QIV-R and QIC-C). A t-test will be used to assess statistical significance of the effects of QIV-R and QIC-C (as compared to reference) as well as the difference in those effects.

Seroconversion (coded as 1 if the post/pre vaccination titre ratio is at least 4, 0 otherwise) will be compared using logistic regression with the explanatory variable being the type of vaccine (reference QIV-E, separate parameter for QIV-R and QIC-C). A t-test will be used to assess statistical significance of the effects of QIV-R and QIC-C (as compared to reference) as well as the difference in those effects.

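### The primary t-test is on an unnamed coefficient of an interaction model, which read literally is the effect in the infrequently vaccinated only, and the two primary comparisons have no order or success rule

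*Combined protocol and SAP*

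**What the plan says.** Section 6.1 states the primary objective as a "better antibody response against A(H3N2) viruses than either standard egg-grown vaccine (QIV-E) or cell-based vaccines (QIV-C". After the adjusted group GMTs it lists two between-arm differences, QIV-R versus QIV-E and, in parallel form, "Difference in log-titres between the QIV-R and QIV-C, adjusted for vaccination history and baseline titre". Neither is ranked above the other.

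Section 13.4.1 takes the model from section 13.3 and says: "A t-test (on a model parameter) will be used to assess statistical significance of the effects of QIV-R versus QIV-E and QIV-C". It gives no coefficient, sidedness, order or rule for combining the two results.

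The section 13.3 model contains products of vaccine and vaccination history. The term b_R-add is defined as "Expected additional effect of QIV-R in the frequently vaccinated", and b_C-add is the matching term for QIV-C. For the power calculation, "The primary outcome measure was taken to be the effect of the QIV-R as compared to the QIV-E", which section 13.3 equates with b_R.

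Section 13.2 gives the aim as "to test whether QIV-R offers superior immunogenicity independent of vaccination history". It describes a test, at alpha 0.05, of superior response among those "receiving QIV-R versus QIV-E or QIV-C (one-sided test for the parameter". Section 4.2.1 says the study is powered primarily on the immunogenicity "of QIV-R compared with QIV-E, and will also assess QIV-R compared with QIV-C".

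**The concern.** When a model includes vaccine-by-history products, the main-effect coefficient for a vaccine is its effect in the reference stratum, here the infrequently vaccinated. A t-test on b_R therefore uses only half of the vaccine comparison and answers a narrower question than the one in section 13.2. Section 13.3 adds to the ambiguity by calling b_R adjusted for prior vaccination frequency, although b_R-add makes it stratum-specific. An analyst following section 13.4.1 could defensibly report either the stratum coefficient or an average over strata, and the two have very different power on the same data.

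The second gap is the success rule. Either of the two primary comparisons could be taken as enough for a superiority claim, or both could be required. The error rate and the power differ between these readings, and section 13.4.1 does not choose.

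**Working it through.** **Inputs (sections 13.2 and 13.3).** b_0 = 1.1, b_baseline = 0.8, b_priorvax = −0.2, b_C = 0.25, b_R = 0.5, b_C-add = 0, b_R-add = 0.2. Baseline log-titre N(3.7, 1), error N(0, 1), 55 per arm per history stratum (cell), alpha 0.05. Titres are coarsened to two-fold intervals, with values below 10 set to 5. Logs are natural, since e^0.5 = 1.65, the ratio in the power table.

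**Contrasts.**
- Infrequent stratum: QIV-R vs QIV-E is b_R = 0.5; QIV-R vs QIV-C is b_R − b_C = 0.25.
- Averaged over strata: QIV-R vs QIV-E is b_R + b_R-add/2 = 0.5 + 0.1 = 0.6; QIV-R vs QIV-C is (b_R − b_C) + (b_R-add − b_C-add)/2 = 0.25 + 0.1 = 0.35.

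**Hand check, ignoring coarsening.** The standard error is √(2/55) = 0.1907 for a stratum contrast and √(1/55) = 0.1348 for an averaged one. One-sided power is Φ(effect/SE − 1.645):
- b_R: Φ(2.622 − 1.645) = 0.836
- b_R − b_C: Φ(1.311 − 1.645) = 0.369
- averaged QIV-R vs QIV-E: Φ(4.450 − 1.645) = 0.997
- averaged QIV-R vs QIV-C: Φ(2.596 − 1.645) = 0.829

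Coarsening lowers these slightly.

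**Reproducing the plan's figure.** Simulating the section 13.3 model with coarsening (20,000 runs) gives power for b_R of 0.808 one-sided and 0.709 two-sided at 55 per cell. The plan's table gives 0.810 and 0.712.

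**Same model, 55 per cell, with coarsening** (stratum rows 20,000 runs, averaged rows 5,000 runs):

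| Tested contrast | Sides | R vs E | R vs C | Both | Either |
|---|---|---|---|---|---|
| Infrequent stratum | one | 0.808 | 0.345 | 0.325 | 0.828 |
| Infrequent stratum | two | 0.709 | 0.240 | 0.220 | 0.730 |
| Averaged over strata | one | 0.996 | 0.807 | 0.806 | 0.996 |
| Averaged over strata | two | 0.990 | 0.709 | 0.707 | 0.991 |

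A second run gave 0.791 for the averaged one-sided QIV-R vs QIV-C test, so about 80% is a fair summary.

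**Sensitivity to the interaction.** Averaged one-sided QIV-R vs QIV-C power is 0.681 with b_R-add = 0.1 and 0.551 with b_R-add = 0.

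**Error rate when all three vaccines are equal.** The two tests share the QIV-R arm, so with equal arms their correlation is 0.5. P(both > 1.645) = 0.0122, hence P(either > 1.645) = 0.05 + 0.05 − 0.0122 = 0.0878. With two-sided 5% tests, P(either > 1.960) = 0.0454. Simulation of the full model gave 0.087 and 0.046.

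**The 74% sentence.** Section 13.3 attaches 74% two-sided power to about 330 subjects, which is 6 × 55. Its table gives 0.712 at 55 per cell; 0.741 is the row for 60 per cell, or 6 × 60 = 360 subjects.

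**The case against.** Much of the intended priority is already in the documents. Sections 4.2.1 and 13.3 put QIV-R versus QIV-E first, and section 13.2 gives a one-sided alpha of 0.05. That stands, and it limits the gap: what is missing is the carrying of these choices into sections 6.1 and 13.4.1, where the comparisons are listed and tested. A priority for sizing is not a testing rule.

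A reader might infer that the trial really has 33% power instead of 80%. The documents do not support this. The plan claims 80% only for QIV-R versus QIV-E, never for winning both. The 33% also needs both wins to be required and both tests to be on the infrequent-stratum coefficients; on averaged contrasts, winning both has about 80% power. A fit without interactions gives nearly the same as the averaged contrasts (0.996, 0.796, 0.795 and 0.997).

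A reader might also infer that the error rate is inflated as the plan stands. It is inflated only if tests are one-sided at 5%, either win suffices, and there is no true difference in either comparison. It is at most 5% if both wins are required.

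The basis of 55 per cell is slightly cautious, since section 12.4 plans to replace participants who miss V2. At 60 per cell, both and either become about 35% and 86% on the stratum coefficients, which does not change the picture.

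Finally, sections 6.1 and 13.4.1 name no A(H3N2) assay virus, although section 7.4.4 lists two. One might infer that the primary antigen could be picked once titres are known. Hypothesis 2 in section 5.2 points to a wild-type-like virus, and the cell- to egg-grown titre ratios of secondary objective 1, with section 10.1, imply that both viruses are titrated. This is missing detail, and the documents give no figure for its effect.

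**Conclusion.** The point holds for the definition of the primary test. Read literally, the coefficient powered in section 13.3 and available to section 13.4.1 is the effect in the infrequently vaccinated, which does not match the aim in section 13.2. On the plan's parameters at 55 per cell and one-sided 5%, the choice of contrast moves QIV-R versus QIV-E from about 81% to 99.6%, QIV-R versus QIV-C from about 35% to 80%, both from about 33% to 80%, and either from about 83% to 99.6%. The averaged QIV-R versus QIV-C figure rests on b_R-add = 0.2 and falls to about 55% at zero.

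The absent success rule leaves a false-claim rate of about 9% under its least favourable reading and no inflation under the others. The 74% two-sided figure is a plain mismatch with the plan's own table. None of this shows that the trial is too small for the comparison it was sized on.

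**What to change.** 1. In section 13.4.1, name the primary tests as the stratum-averaged contrasts: b_R + b_R-add/2 for QIV-R versus QIV-E, and (b_R − b_C) + (b_R-add − b_C-add)/2 for QIV-R versus QIV-C. In section 13.3, restate power for both, with sensitivity to b_R-add.
2. In sections 6.1 and 13.4.1, test in fixed sequence: QIV-R versus QIV-E at one-sided 0.05 (carried over from section 13.2), then QIV-R versus QIV-C at the same alpha only if the first succeeds. This follows the priority in sections 4.2.1 and 13.3. Requiring both wins would also control error.
3. In section 13.3, correct the two-sided power for b_R at 55 per cell from 74% to 71.2%.
4. As a minor clarification, name the cell-type A/Darwin/6/2021-like virus as the primary A(H3N2) assay antigen in all arms, in line with Hypothesis 2, and report the egg-type A/Darwin/9/2021-like virus as secondary.

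The cost is text and a restated power paragraph, with no change to sample size or visits. Both viruses appear to be titrated already, so no extra assay is expected. The downside of the sequence is that QIV-R versus QIV-C is not confirmatory if the first test fails. On the averaged contrasts that costs almost nothing: 0.806 for passing both against 0.807 for QIV-R versus QIV-C alone. The changes should be made before any post-vaccination titres are seen by arm.
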